5.1.1 Retesting During Screening or Lead-in Period

Laboratory parameters and/or assessments that are included in [Table 5.1-1](#), Screening Procedural Outline may be repeated in an effort to find all possible well-qualified subjects. Consultation with the Medical Monitor may be needed to identify whether repeat testing of any particular parameter is clinically relevant.

5.2 Study Materials

- NCI CTCAE version 4.0
- Nivolumab IB
- Pharmacy Information Sheets
- Laboratory manuals for collection and handling of blood (including biomarker and immunogenicity) and tissue specimens;
- Site manual for operation of IVRS, including enrollment worksheets
- Manual for entry of local laboratory data
- Pregnancy Surveillance Forms
- PRO Instruments
- Manual describing process of sending images to corelab

5.3 Safety Assessments

At baseline, a medical history will be obtained to capture relevant underlying conditions. The baseline examinations should include signs and symptoms, weight, height, ECOG Performance Status, BP, HR and temperature should be performed within 72 hours prior to first dose. Concomitant medications will also be collected from within 14 days prior to first dose and through the study treatment period (See [Table 5.1-1](#) and [Table 5.1-2](#)).

Baseline local laboratory assessments should be done within 14 days prior to the first dose and include: CBC w/differential, LFTs (ALT, AST, total bilirubin, alkaline phosphatase), BUN or serum urea level, creatinine, Ca, Mg, Na, K, Cl, LDH, glucose, and, if clinically indicated, urine cytology. Amylase, lipase, TSH, Free T4, Free T3, and Hep B and C testing (HBV sAg and HCV RNA or Ab) should be done within 28 days. Pregnancy testing for WOCBP (done locally) to be done within 24 hours prior to first dose, and then every 4 weeks (+ or – 1 week) regardless of dosing schedule, and at each safety follow up visit (Follow up visits 1 and 2). See [Table 5.1-1](#), [Table 5.1-2](#), and [Table 5.1-3](#).

On-study local laboratory assessments should be done within 72 hours prior to each dose through Week 23 visit and every alternative dose thereafter. Liver function tests (AST, ALT, ALP, T. Bili) will be analyzed within 72 hours prior to each dose throughout the treatment period. Labs should be reviewed by investigator prior to treatment. Subjects will be evaluated for safety if they have received any study drug. Adverse events (AE) assessments will be performed continuously during the treatment phase. During the safety follow-up phase ([Table 5.1-3](#)) AE assessments

should be done in person. Once subjects reach the survival follow-up phase, either in-person visits or documented telephone calls or emails to assess the subject's status are acceptable.

Adverse events and laboratory values will be graded according to the NCI-CTCAE version 4.0.

On-study weight, ECOG performance status, and vital signs should be assessed at each on-study visit prior to nivolumab/placebo dosing. Vital signs should also be taken as per institutional standard of care prior to, during and after dosing. The start and stop time of the nivolumab infusion should be documented. Physical examinations are to be performed at treatment visits as clinically indicated. If there are any new or worsening clinically significant changes since the last exam, report changes on the appropriate non-serious or serious adverse event page.

Additional measures, including non-study required laboratory tests, should be performed as clinically indicated or to comply with local regulations. Laboratory toxicities (eg, suspected drug induced liver enzyme elevations) will be monitored during the follow-up phase via on site/local labs until all study drug related toxicities resolve, return to baseline or are deemed irreversible.

Oxygen saturation by pulse oximetry (optional) may be obtained prior to each dosing and at any time a subject has any new or worsening respiratory symptoms. If obtained, accurate recording and documentation of oxygen saturation at two different activity levels is important because drug-related pulmonary toxicity can present initially as lower than baseline oxygen saturation. A reading at rest and on exertion should be obtained at each time point. The extent of the exertion should be based on the judgment of the investigator, but should remain consistent for each individual subject throughout the study. If the subject's status changes, the investigator can alter the extent of exertion based on their medical judgment. If a subject shows changes on pulse oximetry or other pulmonary related signs (hypoxia, fever) or symptoms (eg, dyspnea, cough, fever) consistent with possible pulmonary adverse events, the subject should be immediately evaluated to rule out pulmonary toxicity. An algorithm for the management of suspected pulmonary toxicity can be found in the nivolumab Investigator's Brochure.

Some of the previously referred to assessments may not be captured as data in the eCRF. They are intended to be used as safety monitoring by the treating physician. Additional testing or assessments may be performed as clinically necessary or where required by institutional or local regulations.

5.4 Efficacy Assessments

Study evaluations will take place in accordance with the flow charts in [Section 5](#). Baseline disease assessments should be performed within 28 days prior to randomization utilizing CT or MRI. In addition to chest, abdomen, pelvis, upper urinary tract, and all known sites of resected disease (including cystoscopy in subjects with upper GU primaries who still have bladder intact) should be assessed at baseline. Brain imaging (MRI except where contraindicated in which CT scan is acceptable) must be completed within 28 days prior to randomization for subjects with clinical suspicion of or known history of brain/leptomeningeal metastases at screening. Of note, screening cystoscopy in subjects who have an intact bladder should occur within 60 days prior to randomization. All suspect lesions identified during screening radiographic procedures should be

discussed with the Medical Monitor prior to randomization. Subjects will be evaluated for presence or continued lack of tumor until non-urothelial tract recurrence as below:

- Non-cystoscopy tumor imaging assessments will occur every 12 weeks from the date of first dose to Week 96 (ie, Week 12, 24, 36, 48, 60, 72, 84, 96; +/- 1 week), then every 16 weeks from Week 96 to Week 160 (ie, Week 112, 128, 144, 160; +/- 2 weeks), then every 24 weeks until non-urothelial tract recurrence or treatment is discontinued (whichever occurs later) for a maximum of 5 years (ie, Week 184, 208, 232, 256; +/- 4 weeks).
- Non-cystoscopy tumor imaging assessments: CT of chest, and CT or MRI of abdomen, pelvis, upper urinary tract, and all known sites of disease. Use same imaging method as was used at screening/baseline.
- Cystoscopy in subjects with upper GU primaries who still have bladder intact will occur in addition to other tumor imaging assessments every 12 weeks from the date of first dose to Week 48 (ie, Week 12, 24, 36, 48 +/- 1 week), then every 24 weeks from Week 48 to Week 96 (ie, Week 72, 96; +/- 2 weeks), then every 48 weeks until non-urothelial tract recurrence or treatment is discontinued (whichever occurs later) for a maximum of 5 years (ie, Week 144, 192, 240; +/- 4 weeks).

5.4.1 Definitions

Recurrence will be considered as any evidence of pathologic disease as described in [section 5.4.3](#). Subjects that have lymph nodes of 10-14 mm in short axis at baseline, will be considered as having recurrence if those lymph nodes progress to ≥ 15 mm in short axis, or if new pathologic lesions are found. Confirmation of recurrence must be attempted as described in [section 5.4.3](#).

The primary endpoint is DFS is defined as time from randomization until death from any cause or recurrence of tumor as described below:

- **Local, Urothelial Tract:** Any new urothelial carcinoma in the lower or upper urothelial tract, including lesions thought to be a second urothelial carcinoma primary will be considered recurrences.
 - Any new invasive urothelial carcinoma (defined as T2 or greater) in the lower or upper urothelial tract, including lesions thought to be a second urothelial carcinoma primary will be considered recurrences. Low-risk NMIBC will not be reported as a recurrence event, while high- and intermediate-risk NMIBC will be reported as a recurrence event.
 - Treatment with study drug may continue if the subject develops low-risk NMIBC that is removed at cystoscopy. The subject may continue study treatment if the subject develops intermediate-risk NMIBC and if intravesical chemotherapy or BCG is not required. Study treatment must be discontinued in the setting of any high-risk recurrence in the urothelial tract.

Low-risk NMIBC is defined as low-grade lesions or papillary urothelial neoplasms of low malignant potential (PUNLMP; WHO/ISUP 2004 grading system), or TaG1 lesions (WHO 1973 grading system) that are less than 3 cm in diameter.

High-risk NMIBC is defined as any T1 lesion, any lesion containing carcinoma in situ (CIS) either alone or concomitantly with papillary disease (e.g. CIS with Ta/T1 lesions), and any Ta high-grade (TaHG; WHO/ISUP 2004 grading system) or TaG3 (WHO 1973 grading system) lesion.

Intermediate-risk NMIBC is defined as lesions not meeting the criteria of high-risk or low-risk.

For subjects with recurrent urothelial tract disease who are no longer eligible for study treatment, tumor imaging should continue until a non-urothelial tract recurrence is documented.

- **Local, Non-Urothelial Tract:** Any recurrence in pelvic soft tissue or involving pelvic nodes below the aortic bifurcation
- **Distant:** Any non-local recurrence

Suspect lesions: Suspect lesions identified radiographically during tumor assessments will be followed according to the defined schedule to determine if they represent recurrent urothelial cancer. If a suspect lesion is confirmed to be recurrent urothelial cancer on subsequent scans, the date of recurrence will be the date the suspect lesion was first identified. If a suspect lesion is identified during cystoscopy, it should be biopsied to determine if it is high-risk, and if so, would represent recurrent local urothelial cancer.

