5.4.3 Confirmation and Date of Recurrence

The first date when recurrence was observed is taken into account regardless of the method of assessment. Therefore recurrence will be declared for any lesion when:

- If recurrence is unequivocal (eg, multiple new measurable lesions, symptomatic or requires initiation of subsequent treatment prior to confirmation) confirmation with histology/cytology should be attempted, but not required.
- If recurrence is equivocal, lymph node only, solitary lesion, or in the urothelial tract, confirmation with histology/cytology must be attempted. Confirmation of a defined lesion on cystoscopy requires transurethral biopsy and, if necessary, retrograde study and biopsy. If risk of biopsy is too high or biopsy not feasible, either a follow-up CT or MRI scan showing progressive disease or PET/CT demonstrating unequivocal FDG uptake must confirm recurrence. Follow-up (confirmatory) scan should occur 4-12 weeks after the initial scan. The date of initial scan showing recurrence will count as recurrence.
- Any pathological evidence of malignancy denotes recurrence (eg, if scans never attempted). Positive urine cytology (eg, positive Urovision or similar urine assay) alone does not constitute the basis for recurrence of disease. Tumor markers or auto-antibodies alone cannot be used to document recurrence.
- If both pathology and imagining were done and recurrence/malignancy confirmed, the date of recurrence is the date to which ever examination came first.
- When biopsies are performed for the purpose of documenting urothelial cancer recurrence, the pathology reports are to be submitted to corelab for a collect and hold. This includes biopsies performed during cystoscopy.

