## 4 ENDPOINTS

### 4.1 Efficacy Endpoints

#### 4.1.1 *Disease-Free Survival*

Disease-Free Survival is the primary endpoint of the study and will be programmatically determined based on the disease recurrence date provided by the investigator.

The following recurrence types are included in the DFS endpoint:

- Local, urothelial tract: any high- and intermediate-risk NMIBC and any new invasive urothelial carcinoma in the lower or upper urothelial tract (defined as T2 or greater), including lesions thought to be a second urothelial carcinoma primary
- Local, non-urothelial tract: Any recurrence in pelvic soft tissue or involving pelvic nodes below the aortic bifurcation
- Distant: Any non-local recurrence

Low-risk NMIBC will **not** be reported as a recurrence event for the DFS endpoint.

Subjects who die without a reported recurrence will be considered to have recurred on the date of their death.

DFS rate at time  $T$  (e.g. 6 months, depending on the minimum follow-up) is defined as the probability that a subject has no disease recurrence and is alive at time  $T$  following randomization, based on the Kaplan-Meier estimate.

The first on-study non-cystoscopy tumor assessment is scheduled to be conducted at 12 weeks ( $\pm 1$  week) from the date of first dose. Subsequent non-cystoscopy tumor assessments are scheduled every 12 weeks ( $\pm 1$  week) up to Week 96, then every 16 weeks ( $\pm 2$  weeks) up to Week 160, then every 24 weeks ( $\pm 4$  weeks) until non-urothelial tract recurrence or treatment is discontinued (whichever occurs later) for a maximum of 5 years.

[figure not shown]
Cystoscopy in subjects with upper GU primaries who still have bladder intact will occur in addition to other tumor imaging assessments every 12 weeks ( $\pm 1$  week) from the date of first dose to Week 48, then every 24 weeks ( $\pm 2$  weeks) up to Week 96, then every 48 weeks ( $\pm 4$  weeks) until non-urothelial tract recurrence or treatment is discontinued (whichever occurs later) for a maximum of 5 years.

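### Two protocol sentences on declaring recurrence do not match the trial's own DFS rule for low- and intermediate-risk NMIBC: a minor wording inconsistency in the primary endpoint definition

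*Protocol*

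**What the plan says.** The DFS rule is stated directly in both documents. Protocol 5.4.1, under the local urothelial-tract heading, says: "Low-risk NMIBC will not be reported as a recurrence event, while high- and intermediate-risk NMIBC will be reported as a recurrence event". SAP 4.1.1 lists the local urothelial-tract events as "any high- and intermediate-risk NMIBC and any new invasive urothelial carcinoma in the lower or upper urothelial tract (defined as T2 or greater"), and adds that low-risk NMIBC is not a DFS recurrence event. Footnote b to SAP Table 4.1.1-1 confirms this for low-risk disease.

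Other protocol wording is not aligned with that rule:

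- The suspect-lesion paragraph of 5.4.1 says of a lesion found at cystoscopy that "it should be biopsied to determine if it is high-risk, and if so, would represent recurrent local urothelial cancer".
- Section 5.4.3 opens its list with "Therefore recurrence will be declared for any lesion when" and includes the item "Any pathological evidence of malignancy denotes recurrence (eg, if scans never attempted").
- Section 5.4.1 itself begins "Recurrence will be considered as any evidence of pathologic disease as described in" section 5.4.3, so it sends the reader there for what recurrence is.
- The lead urothelial-tract bullet of 5.4.1 counts "Any new urothelial carcinoma in the lower or upper urothelial tract, including lesions thought to be a second urothelial carcinoma primary", which is broader than the sub-bullet beneath it.

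Protocol 8.3.1 derives DFS by program from the recurrence date that the investigator supplies. For biopsies done to document recurrence, 5.4.3 says "the pathology reports are to be submitted to corelab for a collect and hold".

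**The concern.** The primary endpoint depends on a site deciding whether a urothelial-tract lesion is a recurrence. A site that follows the suspect-lesion sentence could find an intermediate-risk lesion, conclude that it is not high-risk, and not report it. The rule counts that lesion as an event. A site that follows 5.4.3 could report a biopsied low-grade tumour because it is malignant. The rule says that lesion is not an event.

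The two errors run in opposite directions. The first may also be hard to recover. If an unreported intermediate-risk lesion is followed by more than a single intravesical dose, SAP Table 4.1.1-1 (footnotes a and b) may censor the subject at the last evaluable assessment before that therapy and disregard what follows. The documents supplied do not describe how a lesion's risk group would be verified.

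**Working it through.** **Step 1: the texts side by side, by lesion type.**

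| Lesion | Rule (Protocol 5.4.1 sub-bullet; SAP 4.1.1) | Protocol 5.4.1, suspect lesion | Protocol 5.4.3 |
|---|---|---|---|
| Low-risk NMIBC | not an event | not named; consistent | recurrence if malignant; **mismatch** |
| Intermediate-risk NMIBC | event | not named; **mismatch by omission** | recurrence; consistent |
| High-risk NMIBC | event | recurrence; consistent | recurrence; consistent |

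The low-risk group includes papillary neoplasms of low malignant potential, which a site may not regard as malignancy. The 5.4.3 mismatch therefore mainly concerns low-grade or TaG1 carcinoma.

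The lead bullet of 5.4.1 raises a separate question. The NMIBC groups are bladder categories and are not extended to the upper tract here. A new upper-tract carcinoma below T2 is within the lead bullet but not within the T2-or-greater wording.

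**Step 2: reach.** Scheduled cystoscopy applies to upper-tract primaries with an intact bladder (Protocol 5.4). The cap on upper-tract subjects is 0.20 × 700 = 140 (Synopsis). The documents give neither the intact-bladder share nor a rate of low- or intermediate-risk lesions, so no total can be calculated.

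**Step 3: one withheld event.** The DFS analyses are triggered by event counts (Protocol 8.1 and 8.5), so a withheld event moves the date and not the number of events analysed. From Tables 8.1-1 and 8.1-2, the average event rates between months 45 and 60 are:

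- All randomized: (410 − 348)/(60 − 45) = 62/15 = 4.13 per month. One event is 1/4.13 = 0.24 months, about 7 days.
- PD-L1 ≥1%: (162 − 137)/15 = 25/15 = 1.67 per month. One event is 1/1.67 = 0.6 months, about 18 days.

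These take the event as never counted. A later recurrence can still count, so the delay may be shorter. They use an average rate and are approximate.

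**Step 4: one added event with no treatment effect.** The design is two looks with Lan-DeMets O'Brien-Fleming spending, two-sided 2.5%. At information fraction 0.85 the calculation reproduces the plan's nominal levels, 0.01349149 and 0.02108499. With D events, of which one carries no effect, the diluted hazard ratio is exp(ln(HR) × (D − 1)/D).

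| Population | D | Planned HR | Power | Diluted HR | Power | Loss |
|---|---|---|---|---|---|---|
| All randomized | 410 | 0.72 | 85.4% | 0.7206 | 85.2% | 0.2 points |
| PD-L1 ≥1% | 162 | 0.61 | 80.9% | 0.6119 | 80.4% | 0.5 points |

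The base powers are proportional-hazards approximations. The plan's 87% and 80% rest on its cure-rate model with delayed effect, so only the differences are used here.

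One lesion is 1/410 = 0.24% of the planned events overall and 1/162 = 0.62% in PD-L1 ≥1%.

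**The case against.** The strongest reply is that the rule is already explicit. It stands in Protocol 5.4.1, is repeated in SAP 4.1.1 and is confirmed in a table footnote. The suspect-lesion sentence comes shortly after the rule in the same section. Section 5.4.3 is headed as covering confirmation and dating, and its parenthesis about scans suggests that the item concerns type of evidence. A site would have to follow a general or incomplete sentence over a specific one. This largely stands, and it is why the point is minor. It does not remove the point, because 5.4.1 refers to 5.4.3 for what recurrence is and because the suspect-lesion sentence frames the biopsy question as high-risk or not.

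A reader might infer more than the documents support:

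- *That intermediate-risk lesions are expressly excluded at cystoscopy.* The sentence gives a sufficient condition and not a necessary one, so this is an omission.
- *That SAP 4.1.3 makes low-risk NMIBC a DFS event.* That section does include low-risk NMIBC when it defines local urothelial-tract recurrence, and Table 4.1.1-1 counts such recurrence for DFS. But SAP 4.1.3 only lists what is not an event for non-urothelial tract recurrence-free survival (NUTRFS), and SAP 4.1.1 excludes low-risk disease from DFS. No DFS or NUTRFS event changes.
- *That withheld events reduce power.* They do not if 410 and 162 events are still reached; they delay the analysis.
- *That nobody checks risk group.* Protocol 7 mentions adjudicated events in general terms, and the CRF guidelines and adjudication documentation are not in the file. One can say only that the documents supplied show no such check.
- *That one arm is favoured.* The trial is double-blind, so the expected effect is noise or lost events.

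**Conclusion.** The inconsistency is real and concerns which lesions sites report as primary-endpoint events. The intended rule can be identified and no sample size, alpha or power figure is shown to be wrong. This is a wording inconsistency in the endpoint definition, of minor severity.

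The total effect cannot be derived, because the documents give no lesion rate. Judging it probably small rests on two things: the explicit rule makes misreporting unlikely, and most of the exposure lies in upper-tract subjects who still have a bladder. The per-lesion figures assume, for a withheld event, that it is never counted and that the average late event rate applies; for an added event, that it carries no treatment effect and that hazards are proportional. Withheld and added events are alternatives for any one lesion and should not be summed.

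**What to change.** For endpoint reporting only:

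1. Protocol 5.4.1, suspect lesions: refer to *high- or intermediate-risk*, as in the rule.
2. Protocol 5.4.3, item on pathological evidence: add *except low-risk NMIBC as defined in 5.4.1*.
3. Protocol 5.4.1, lead urothelial-tract bullet: the sponsor should reconcile it with the T2-or-greater wording and say how a new upper-tract carcinoma below T2 is counted. This needs a decision and is more than an edit.
4. Protocol 3.5 requires study drug to stop for recurrence, while 5.4.1 lets treatment continue in some intermediate-risk NMIBC. Naming intermediate-risk lesions as recurrence in item 1 touches this conflict, so the sponsor must reconcile the two passages at the same time. No treatment rule is proposed here.
5. Before database lock and while blinded, check the urothelial-tract pathology reports that were submitted against the rule and query mismatches. This check has a limit: 5.4.3 asks for reports from biopsies done to document recurrence, so reports on lesions that a site judged not to be recurrence may not have been submitted.
6. Optional tidy-up: in SAP 4.1.3, write *lesions* in place of *recurrence* for the urothelial-tract group, so that the term keeps one meaning.

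The cost is two short protocol edits, two sponsor decisions (items 3 and 4), one optional SAP edit, and a blinded data review. Retrieving reports that were never submitted would be additional work.

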5.4.2 Methods of Measurements

- CT and MRI are an essential part of the work-up to establish recurrence. The following imaging assessments should be performed at pre-specified intervals: CT of chest, and CT or MRI of abdomen, pelvis, upper urinary tract and all known or suspected sites of disease (including cystoscopy in subjects with upper GU primaries who still have bladder intact).
- CT scans should be acquired with 5 mm slices with no intervening gap (contiguous).
- Should a subject have a contraindication for CT IV contrast, a non-contrast CT of the chest and a contrast enhanced MRI of the abdomen and pelvis may be obtained. MRIs should be acquired with slice thickness of < 5 mm with no gap (contiguous).
- Every attempt should be made to image each subject using an identical acquisition protocol on the same scanner for all imaging time points.
- PET alone will not be considered for the disease assessment. Complementary CT and/or MRI or biopsy must be performed in such cases.
 - Note: Use of CT component of a PET/CT scanner:

Combined modality scanning such as with FDG-PET/CT is increasingly used in clinical care, and is a modality/technology that is in rapid evolution; therefore, the recommendations outlined here may change rather quickly with time. At present, low dose or attenuation correction CT portions of a combined FDG-PET/CT are of limited use in anatomically based efficacy assessments and it is therefore suggested that they should not

be substituted for dedicated diagnostic contrast enhanced CT scans for anatomically based tumor assessments. However, if a site can document that the CT performed as part of a FDG-PET/CT is of identical diagnostic quality to a diagnostic CT (with IV and oral contrast) then the CT portion of the FDG-PET/CT can be used for tumor assessments. Note, however, that the FDG-PET portion of the CT introduces additional data which may bias an investigator if it is not routinely or serially performed

